## 8. INFERENTIAL PRINCIPLES

Only the test on the primary criterion, on which is based the sample size justification, may lead to a causal interpretation. All other statistical results are to be regarded as exploratory. Statistical tests will be two-sided and the significance level will be set to 5 %.

In order to obtain statistical modelling convergence and balance number of randomised patients, Poland (with only four randomised patients) will be grouped with the country that randomised the second lowest number of patients (Hungary). Categorical variable “Country” will be analysed with 4 levels for stratified statistical tests and statistical modeling: Italy, Spain, Czech Republic and Hungary.

## 9. DEVIATIONS

A final data review meeting will be held, prior to database lock, in order to review protocol deviations. These will be classified as minor or major.

A protocol deviation will be considered as major when it is likely to bias significantly the treatment effect estimate based on the primary efficacy criterion.

Major protocol deviations and other sources of bias for primary criterion analyses, as well as additional reasons of exclusion from analysis sets will be identified using the list of pre-defined reasons for exclusion from analysis sets for the study described in a specific document “Predefined reasons for exclusion from analysis sets“ separately from the statistical analysis plan.

A listing of all deviations and a listing of additional reasons for exclusion from statistical analysis will be provided for all randomised patients, including the type (major/minor) as validated during the data review meeting. This listing should be provided prior to the database lock and the randomisation code release.

The number and percentage of patients with major protocol deviations will be tabulated by treatment group and type of major protocol deviations on the randomised patients set defined in section 7. The number and percentage of patients with minor protocol deviations will be also tabulated by treatment group and type of minor deviations on the randomised patients set.

The number and percentage of patients with reason of exclusion from analysis sets will be tabulated by treatment group and type of reason of exclusion on the randomised patients set.

## 10. HANDLING OF MISSING DATA AND ANALYSIS OF DROP-OUTS

### 10.1. DROP-OUTS

Results of criteria reported over time will be presented on the observed cases (OC).

### 10.2. REPOSITIONING OF VISITS

For premature withdrawals, patients' data at the end of study visit will be imputed to the next expected visit (Observed Case approach). For example, if a patient drops out of the study after Visit 6 (Week 12), then the end of study visit will implement the visit 7 (Week 16).

Unscheduled measurements will be taken into account for analysis in case of missing original measurement.

Unscheduled measurements will be taken into account for individual detection of abnormalities.

In case of several post-baseline retests around a same visit, the first available measurement at the visit will be kept for all analyses.

### **10.3. MISSING DATA (OTHER THAN DROP-OUT)**

- **For Safety analyses:**

For safety analyses, missing values will be replaced by corresponding value of repositioned unscheduled measurement if any.

For laboratory data, in the case that an upper limit is mentioned in the associated character variable, missing numerical value will be replaced by the limit mentioned in the character variable. (For lower limit, missing numeric value will be replaced by the lower limit).

Example: for a measure of ALAT with a character variable “<6”, missing numeric value will be replaced by 6.

**Missing body weight:** for creatinine clearance estimation, missing body weight will be replaced by the body weight measured at the nearest visit.

Replacement of missing or incomplete dates presented hereafter is defined in a conservative approach.

- **Missing dates of first or last trial drug intake**

Missing dates of the first trial drug intake will be considered equal to the inclusion day.

Missing dates of last trial drug intake will be discussed by the members of the data review meeting and extrapolated using all information recorded.

- **Missing dates of start of adverse event**

In case of completely missing date, it will be estimated by the date of first intake of study drug

If the day and the month are missing,

- If the year is the same as the year of first intake, it will be estimated by the date of first intake of study drug
- If the year is prior to the year of first intake, it will be estimated by the 31 December
- If the year is after the year of first intake, it will be estimated by the 1st January

If only the day is missing,

- If the month/year are the same as the month/year of first intake, it will be estimated by the date of first intake of study drug

- If the month/year are prior to the month/year of first intake, it will be estimated by the last day of the month
- If the month/year are after to the month/year of first intake, it will be estimated by the first day of the month

If after imputation, the estimated start date is after the end date of the adverse event, it will be replaced by the end date of the adverse event

- **Missing dates of end of adverse event**

For adverse events that are not “ongoing” at the end of the study (i.e. with an outcome other than “Not recovered/not resolved” or “Recovering/resolving”):

In case of missing date, it will be estimated by the last available date (last visit or last unscheduled exam date)

If the day and the month are missing,

- If the year is the same as the year of last available date, it will be estimated by the last available date
- If the year is prior to the year of last available date, it will be estimated by the 31 December

If only the day is missing,

- If the month/year are the same as the month/year of last available date, it will be estimated by the last available date
- If the month/year are prior to the month/year of last available date, it will be estimated by the last day of the month

If after imputation, the estimated end date is before the start date of the adverse event, it will be replaced by the start date of the adverse event

- **Missing severity or relationship to study drug of an adverse events**

If the maximal severity of an AE, as reported by the investigator, is missing, a maximal severity “severe” will be imputed.

If the relationship to study drug, as reported by the investigator, is missing, a relationship “suspected” will be imputed.

- **Concomitant medications**

When the start date is partially or completely missing, the same rules as for start and end date of adverse event will be applied, except in case of confirmation of previous medication in the CRF (ticked box) that will be estimated at the earliest date.

## 11. DESCRIPTIVE STATISTICS

Summary statistics will be presented by treatment group and visit when appropriate, and will consist of values for:

- quantitative parameters: number of missing data, number of patients, mean, standard deviation (sd), median, lower and upper quartiles, minimum and maximum, 95% confidence interval around the mean (when relevant)
- qualitative parameters: number of missing data, and number and percentage of patients.

Mean changes and standard error of mean (SEM) will be also represented graphically from baseline over time for relevant criteria.

Calculated statistics (mean, sd, median, lower and upper quartiles and 95% confidence interval) will display at most one more significant figure than the observed data.

For percentages, one decimal digit will be given.

Individual data listings will be provided for all analysed criteria.

## 12. DISPOSITION OF PATIENTS

The number of screened patients (who have signed an informed consent) and randomised patients, and reasons for non randomisation will be provided on the Screened patients set.

The number of patients in each analysis set detailed in section 2 will be provided by treatment group and by country and centre for randomised patients.

The number of randomised patients by visit done will be also tabulated by treatment group for randomised patients.

The number and percentage of patients who withdrew prematurely from the study after their randomisation will be provided by treatment group and reasons of drop out on the randomised patients set.

## 13. DEMOGRAPHIC AND OTHER BASELINE CHARACTERISTICS

Before the first trial drug intake, medical and surgical history, demographic data (gender, age, weight, height and BSA) and disease characteristics (left atrial area in  $\text{cm}^2$ , left ventricular ejection fraction in %, duration of current AF up to selection visit (days), time from first

documented persistent AF up to selection visit, time from heart failure diagnosis up to selection visit, NYHA grade) will be described by treatment group on the Full Analysis Set.

These data, except disease characteristics and baseline efficacy criteria will also be described on the Safety set.

If more than 10.0% patients of the FAS are excluded from the Per Protocol Set, demographic data, disease characteristics and baseline efficacy criteria will be repeated on the PP Set.

The age in years will be calculated as the integer part of [(reference start date\* - date of birth)/365.25]. \*See appendix 1

For listings of individual data, the age presented for randomised and non treated patients will be (date of randomisation - date of birth) and the age for not randomised patients will be (date of informed consent signature dates - date of birth).

The BMI will be calculated as weight (kg) / [height (m)] rounded to 1 decimal place.

Time from first documented persistent AF and time from heart failure diagnosis up to selection visit will be calculated in months as (selection visit date – event date +1)/30.4, rounded to one decimal place.

Body weight, BSA, left atrial area and left ventricular ejection fraction at screening and inclusion visits will be described by treatment group only for baseline values (*i.e.* last values measured before the first application of study drug).

Concomitant diseases at selection, as well as medical and surgical history will be tabulated descriptively by treatment group using the MedDRA System Organ Classes and preferred terms on the Safety Set.

Concomitant treatments taken before first study drug intake date will be tabulated descriptively (number and percentage of patients) by treatment group on the Safety Set. They will be classified by therapeutic area according to the WHO-DRUG dictionary using the "anatomical therapeutic chemical" (ATC) classification, by WHO-DRUG ATC1 and ATC2 codes.

Concomitant treatments taken before first study drug intake date and linked to the study pathology will be also tabulated as above.

Any factor which could bias the treatment effect estimate, like demographic data or any other baseline characteristics will be cautiously examined in order to determine whether the randomisation failed and affect the interpretation of the primary results. If this descriptive analysis provides any clues on potential imbalances, further statistical investigations will be carried out.

## 14. ANALYSIS OF EFFICACY

Unless otherwise specified, the efficacy analysis will be performed on the FAS. Baseline values will be the latest value measured before the first study drug intake.

### 14.1. PRIMARY CRITERION

The primary efficacy criterion is the time to first recurrence of AF or atrial flutter emergence. The time to first recurrence of AF or atrial flutter emergence is defined by the time between the date of ECV visit (visit 3) and the date of the first recurrence of AF or atrial flutter emergence over the period V3-V9.

The first recurrence of AF or atrial flutter is defined as the first episode of AF (symptomatic or not) or atrial flutter emergence lasting for at least 10 minutes from visit 3.

For randomised patients with spontaneous cardioversion before ECV, the recurrence of AF or the emergence of atrial flutter will be assessed from visit 3 (week 5).

The primary efficacy criterion will be calculated in a conservative approach:

- If first TTEM measurement is the first confirmed AF/flutter alert then the day after the end date of Holter will be considered as the onset day of first AF recurrence or atrial flutter emergence.
- If TTEM measurement is not available the day before the first confirmed AF/flutter alert, then the day after the previous TTEM will be considered as the onset day of first AF recurrence or atrial flutter emergence.
- If an AF/flutter alert in TTEM measurement was not checked at least 10 minutes after on the same day, it will be considered as the onset day of the first AF/flutter only if AF/flutter is confirmed with the next measurement.

If the patient has a premature EOT at a visit X (or in between visits X-1 and X), the censoring time will be at visit X. If the patient took prohibited treatment leading to non recurrence/non emergence prior to premature EOT, the censoring time will be the start date of the prohibited treatment.

If no recurrence of AF or atrial flutter emergence can be ascertained by last measurement day and the patient has not already been censored according to the rule described above, the patient will be right-censored at the last measurement day.

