### **Primary efficacy criterion**

The primary criterion is the time to first Atrial Fibrillation recurrence or Atrial Flutter emergence defined by the time to first episode of Atrial Fibrillation or atrial flutter lasting for at least 10 minutes during the follow up of 20 weeks after visit 3 (ECV visit).

The cardiac monitoring is performed using:

- A 7-day continuous ECG ambulatory recording (Holter ECG) between visit 3 (ECV visit) and visit 4 (week 5) in patients cardioverted to sinus rhythm.
- A Trans Telephonic ECG Monitoring (TTEM):

\* before protocol amendment PA05: with a daily transmission from week 6 to week 8; then every two days from week 9 to week 24, and at anytime in case of AF symptoms

\* after protocol amendment PA05: with one transmission per week from the day of visit 4 (end of week 5) to visit 9 (week 24).

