**V5 et V8 were cancelled in the amendment PA05**

## 7. ANALYSIS SETS

The following analysis sets will be defined:

- **The Screened patients Set** which consists of all patients who have signed an informed consent,
- **The Randomised Patients Set** which consists of all patients who have signed an informed consent, and are assigned a treatment number,
- **The Safety Set** composed of all randomised patients having taken at least one dose of the study treatment. This set will be used to perform analyses of Safety.
- **The Full Analysis Set (FAS)** composed of all randomised patients having received at least one dose of the study treatment and with a successful cardioversion observed at visit 3. A successful cardioversion will be defined as either spontaneous cardioversion before V3 or successful ECV performed at V3 (early relapse within the observation period after ECV will be considered as non successful). This set will be used to perform analyses of Efficacy.
- **The Per Protocol Set (PP)** which is the subset of the Full Analysis Set composed of all FAS patients without any major protocol deviation or other source of bias for primary criteria analyses. This set will be used to perform the supportive analysis of the primary efficacy criterion.

Patients from Randomised Patients Set, Safety Set, Full Analysis Set or PP set will be analysed as treated (*ie* as treatment actually received at the randomisation). In case of error of treatment dispensation during the study period, the assignment of patient treatment group will be discussed during the data review meeting.

Randomised patients not treated will be analysed as randomised (*ie* as treatment allocated at the randomisation).

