### **14.1.1. Primary Analysis**

The primary criterion, time to first recurrence of AF or atrial flutter emergence, will be described using survival curves according to the Kaplan Meier method. Survival curves will be performed by treatment group. The time to first recurrence of AF or atrial flutter emergence will be compared between treatment groups using with the Log rank test.

The distribution of time to first recurrence of AF or atrial flutter emergence will be described by treatment group using Kaplan-Meier methods, reporting Q1, Q3, median, and the 95% confidence interval (CI).

Survival rates (patients still in sinus rhythm) will be described by treatment group at several time points (including 1 week, 1, 2, 3 and 4 months).

Hazard ratios and 95% confidence intervals (based on the Wald test) will be estimated with a Cox regression model. The PHREG procedure in SAS with option TIES=EXACT will be used to fit the Cox proportional hazards model.

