#### **14.2.3. Time to first AF recurrence / flutter emergence less than 10 minutes during TTEM period**

The time to the first AF recurrence / flutter emergence less than 10 minutes will be analysed as the primary analysis.

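### SAP 14.1 censors premature EOT at a visit X whose date is not defined, ahead of the last-measurement-day rule, so unrecorded time can count as event-free; the effect is modest

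*SAP*

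**What the plan says.** SAP 14.1 gives two censoring rules for event-free patients.

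- Early stoppers: for "premature EOT at a visit X (or in between visits X-1 and X), the censoring time will be at visit X".
- Everyone else: right-censoring at the last measurement day, but only where "the patient has not already been censored according to the rule described above". The visit-X rule therefore comes first.

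No date is attached to visit X, and EOT is not in the abbreviation list (section 5). Section 10.2 says that a withdrawn patient's "data at the end of study visit will be imputed to the next expected visit", with a dropout after V6 moved to V7 as the example. That relabels visit data; it does not fix a date for a survival time. The reference-date conventions in Appendix 1 do not settle it either.

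Rhythm for the endpoint comes from a 7-day Holter after V3 and then TTEM (section 6). TTEM is weekly after PA05; before PA05 it ran "with a daily transmission from week 6 to week 8; then every two days from week 9 to week 24". The note under the flow chart adds that "V5 et V8 were cancelled in the amendment PA05".

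A further sentence in 14.1 begins "If the patient took prohibited treatment leading to non recurrence/non emergence prior to premature EOT" and moves censoring to the start of that treatment.

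**The concern.** For a patient who stops between visits, visit X lies after the stop. If the last Holter or TTEM recording is earlier still, the interval up to visit X is counted as sinus rhythm although nobody observed it. Two programmers could also derive different censoring dates from the same text.

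The derivation feeds the log-rank test, which section 8 makes the only test open to causal interpretation. It also feeds the hazard ratio, the sinus-rhythm rates that 14.1.1 reports at 1 week and 1 to 4 months, and the per-protocol repeat in 14.1.2. The secondary criterion in 14.2.3 ("flutter emergence less than 10 minutes will be analysed as the primary analysis") appears to inherit it, as does the one in 14.2.4.

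There is a minor wording query as well. The prohibited-treatment sentence may name a type of treatment, or it may make censoring depend on whether recurrence followed. It also covers only patients with premature EOT.

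**Working it through.** **Plan's own figure.** Under exponential recurrence the design rates give HR = ln 0.35 / ln 0.15 = 0.553. Freedman's formula gives (1.960 + 0.842)² × (1.553/0.447)² ≈ 95 events. Then 95 / (0.85 + 0.65) = 63.3, so 64 per group, and 64 / 0.85 = 75.3, so 76. Both match section 6. The sample size does not depend on the censoring rule.

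**Longest unrecorded interval, scheduled date, post-PA05** (flow-chart days 35, 84, 112, 168):
- V4 to V6: 84 − 35 = 49 days
- V6 to V7: 112 − 84 = 28 days
- V7 to V9: 168 − 112 = 56 days

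**Simulation assumptions.** 57 patients per arm (135 × 0.85 / 2 = 57.4). Exponential recurrence with hazard −ln(0.15)/140 = 0.01355 per day, and AF persisting once begun. EOT uniform over 140 days, with recording ending at EOT. TTEM events dated to the day after the previous TTEM, as 14.1 requires. The SAP gives no EOT rate and no pre/post-PA05 split. V5 and V8 are assumed at weeks 8 and 20. There were 20,000 replicates, or 10,000 for power.

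**Mean time credited beyond the last recording, per event-free stopper**

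| Schedule | Scheduled date | Attended, 3 days after stopping |
|---|---|---|
| Post-PA05 | 26.6 days | 6.7 days |
| Pre-PA05 | 13.5 days | 4.3 days |

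**Sinus-rhythm rate, visit-X rule v last-recording rule**

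| Case | 2 months | 4 months | 20 weeks |
|---|---|---|---|
| Scheduled, post-PA05, 15% EOT | 43.7 v 42.5% | 19.1 v 18.1% | 16.1 v 15.0% |
| Scheduled, post-PA05, 30% EOT | 45.0 v 42.6% | 20.4 v 18.2% | 17.4 v 15.0% |
| Attended, post-PA05, 15% EOT | 43.0 v 42.5% | – | 15.4 v 15.0% |
| Scheduled, pre-PA05, 15% EOT | 43.6 v 43.1% | – | 15.5 v 15.0% |

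**Against the true rate** S(t) = exp(−0.01355 t). Because TTEM events are dated early, a curve censored at the last recording shows at day t the value of S at the next TTEM day. The table uses the scheduled date, post-PA05, 15% EOT.

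| Day | True S | S at next TTEM | Visit-X rule |
|---|---|---|---|
| 61 | 43.8% | S(63) = 42.6% | 43.7% |
| 91 | 29.1% | S(91) = 29.1% | 30.2% |
| 122 | 19.1% | S(126) = 18.1% | 19.1% |
| 140 | 15.0% | S(140) = 15.0% | 16.1% |

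The visit-X rule adds about 1 point to the third column throughout. At days 61 and 122 the early dating cancels it; at days 91 and 140 it does not.

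**Log-rank test under no effect** (scheduled date, post-PA05; visit-X v last-recording rule; nominal 5% two-sided, 2.5% per tail)

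| EOT by arm | Two-sided | Tail favouring the arm that stops more |
|---|---|---|
| 15% v 15% | 5.0 v 5.0% | – |
| 15% v 10% | 5.0 v 5.0% | 2.9 v 2.7% |
| 20% v 10% | 5.4 v 5.2% | 3.3 v 2.6% |
| 25% v 5%, all within 8 weeks | 6.1 v 5.2% | 4.8 v 2.5% |

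Monte Carlo SE is about 0.11 points per tail. A separate run at 30% v 10% gave a favourable tail of about 4.2 v 2.4%. In the 8-week case the favourable tail under the visit-X rule falls to 3.3% with the attended date (post-PA05) and 3.6% with the scheduled date pre-PA05.

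**Power at the design effect.** With balanced 15% EOT it is 74.5 v 75.3%. A second simulation (1,500 replicates, exponential stopping, scheduled date) gave 81.1 v 75.2% when active stops at 30% and placebo at 10%, and 68.7 v 76.0% the other way round.

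**The case against.** A reader might infer that the visit-X rule biases the reported sinus-rhythm rates upwards. The documents do not support that as a general statement. At 2 and 4 months, with 15% EOT, the rule lands on the true rate and last-recording censoring falls about 1 point below it. This stands as a correction to the direction of bias. It does not defend the rule, because the agreement is two errors cancelling on particular days, and it fails at day 91, at day 140 and at 30% EOT (45.0% v a true 43.8% at day 61).

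The attended date is arguably the more natural reading. Section 10.2 starts from an actual end-of-study visit, and 14.1 itself counts from the date of the ECV visit. On that reading the shift is at most about 0.5 points, against a Kaplan-Meier standard error of about √(0.4375 × 0.5625 / 57) = 6.6 points at 2 months. The flow chart also schedules a 12-lead ECG at V6, V7 and V9, which could document rhythm at an attended visit, although section 6 names only Holter and TTEM for the endpoint. All of this stands, and it is why the point is modest.

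The SAP does not say that TTEM ends with treatment. If a patient stops drug but keeps transmitting, visit X could precede the last recording. Censoring everyone at the last recording would then extend follow-up past EOT and change what is estimated. That stands, and the fix below is limited accordingly.

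Finally, no passage suggests unequal stopping. The imbalance scenarios are illustrations, and the 15% in section 6 is a rate of non-assessable patients, not of early stopping.

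**Conclusion.** The gap is real and of modest consequence. Visit X has no defined date, its rule overrides last-measurement-day censoring, and time without a recording can count as event-free.

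Relative to last-recording censoring at 15% EOT, the shift is up to about 0.5 points (attended date) or about 1 point (scheduled date, post-PA05). At 30% EOT with the scheduled date it is about 2 points. The sign relative to the true rate depends on the time point.

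A reader might also infer that the primary test is invalid. It is not shown to be: with balanced stopping its error rate and power are essentially unchanged. The tilt matters only if stopping is clearly unequal and visit X means the scheduled date. All sizes rest on assumed stopping rates and on recording ending at EOT.

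The prohibited-treatment sentence is a minor wording query and has not been quantified. To call it outcome-dependent censoring would go further than the text, since it may simply name a type of treatment.

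**What to change.** In 14.1, for premature EOT without an event, censor at the last valid rhythm recording on or before the EOT visit. Use the visit date only if that visit was attended and rhythm was recorded there. Define EOT, and remove the precedence of the visit-X rule. This keeps the SAP's choice to end follow-up at EOT and matches its rule for other patients. Report the analysis with the visit-X date, stating which date is used, as a sensitivity analysis.

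Reconcile the prohibited-treatment sentence so that censoring does not depend on later recurrence. Which treatments count is for the sponsor.

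The cost is two reworded sentences, one changed derivation program and slightly less follow-up time. No new data are needed, and the change should be made before the randomisation code is released.
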